### **Other PTs of interest**

Other PTs of interest will be defined as any TEAE with a PT of orthostatic hypotension, fall, dizziness, dizziness postural, or vertigo.

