8.4 Orthostatic Hypotension Evaluations

Orthostatic hypotension will be evaluated at baseline (Day 0), Day 7, and Day 14.

For this determination, the subject will be placed supine for 5 minutes. At the end of that time a manual BP will be assayed three times. The average of these three will be used as the baseline value. The subject will then be asked to stand vertically and two manual BPs will be obtained: the first will be one minute after standing and the second will be three minutes after standing. Orthostatic hypotension will be defined as a decrease in systolic BP of > 25 mmHg from baseline in either of the readings, or a decrease in diastolic BP of > 15 mmHg in either of the readings compared to the baseline average.

In addition to these quantitative measurements, specific comparisons in reported AE rates for terms associated with hypotension will be made. These events will include dizziness, falls, light-headedness, and vertigo.

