5 WARNINGS AND PRECAUTIONS

5.1 Hypotension

Symptomatic hypotension is possible, particularly in patients with severe aortic stenosis. Because of the gradual onset of action, acute hypotension is unlikely.

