6 ADVERSE REACTIONS

6.1 Clinical Trials Experience

Because clinical trials are conducted under widely varying conditions, adverse reaction rates observed in the clinical trials of a drug cannot be directly compared to rates in the clinical trials of another drug and may not reflect the rates observed in practice.

NORVASC has been evaluated for safety in more than 11,000 patients in U.S. and foreign clinical trials. In general, treatment with NORVASC was well-tolerated at doses up to 10 mg daily. Most adverse reactions reported during therapy with NORVASC were of mild or moderate severity. In controlled clinical trials directly comparing NORVASC (N=1730) at doses up to 10 mg to placebo (N=1250), discontinuation of NORVASC because of adverse reactions was required in only about 1.5% of patients and was not significantly different from placebo (about 1%). The most commonly reported side effects more frequent than placebo are reflected in the table below. The incidence (%) of side effects that occurred in a dose related manner are as follows:

	2.5 mg N=275	Amlodipine 5 mg N=296	10 mg N=268	Placebo N=520
Edema	1.8	3.0	10.8	0.6
Dizziness	1.1	3.4	3.4	1.5
Flushing	0.7	1.4	2.6	0.0
Palpitation	0.7	1.4	4.5	0.6

Other adverse reactions that were not clearly dose related but were reported with an incidence greater than 1.0% in placebo-controlled clinical trials include the following:

	NORVASC (%) (N=1730)	Placebo (%) (N=1250)
Fatigue	4.5	2.8
Nausea	2.9	1.9
Abdominal Pain	1.6	0.3
Somnolence	1.4	0.6

For several adverse experiences that appear to be drug and dose related, there was a greater incidence in women than men associated with amlodipine treatment as shown in the following table:

	NORVASC		Placebo	
	Male=% (N=1218)	Female=% (N=512)	Male=% (N=914)	Female=% (N=336)
Edema	5.6	14.6	1.4	5.1
Flushing	1.5	4.5	0.3	0.9
Palpitations	1.4	3.3	0.9	0.9
Somnolence	1.3	1.6	0.8	0.3

The following events occurred in <1% but >0.1% of patients in controlled clinical trials or under conditions of open trials or marketing experience where a causal relationship is uncertain; they are listed to alert the physician to a possible relationship:

Cardiovascular: arrhythmia (including ventricular tachycardia and atrial fibrillation), bradycardia, chest pain, peripheral ischemia, syncope, tachycardia, vasculitis.

Central and Peripheral Nervous System: hypoesthesia, neuropathy peripheral, paresthesia, tremor, vertigo.

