#### **b. Other PTs of interest**

The protocol specified a comparison of AE rates for terms associated with hypotension, defined as dizziness, falls, light-headedness, and vertigo. The definition will be changed to TEAEs with PTs of orthostatic hypotension, fall, dizziness, dizziness postural, and vertigo. The use of PTs and the addition of orthostatic hypotension to the list provides a more precise and comprehensive analysis, as well as allows a direct comparison to a similar analysis conducted for the prior trial (KIT-302-03-01). Note, light-headedness is coded under dizziness as a PT.

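### The SAP's closed list of hypotension-related preferred terms omits hypotension itself and syncope, so a subject whose only such event carries one of those terms is scored as no event in that category's between-arm test

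*SAP*

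**What the plan says.** Protocol 8.4 first defines orthostatic hypotension from supine and standing readings. It then adds that "specific comparisons in reported AE rates for terms associated with hypotension will be made", and says these events will include dizziness, falls, light-headedness and vertigo. That wording leaves the list open.

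SAP 1.3.9b describes the protocol list as a definition: "The protocol specified a comparison of AE rates for terms associated with hypotension, defined as dizziness, falls, light-headedness, and vertigo". It replaces that list with five MedDRA preferred terms (PTs) and gives two reasons. One is that "The use of PTs and the addition of orthostatic hypotension to the list provides a more precise and comprehensive analysis". The other is that the result can be compared directly with a similar analysis in KIT-302-03-01. It adds one coding remark: "Note, light-headedness is coded under dizziness as a PT".

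SAP 6.4 fixes the definition: "Other PTs of interest will be defined as any TEAE with a PT of orthostatic hypotension, fall, dizziness, dizziness postural, or vertigo".

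SAP 7.9 makes this one of eight TEAE categories summarised by arm. Differences between groups are tested by Chi-square, or by Fisher's exact test when expected counts are small.

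**The concern.** The category exists to compare hypotension-related adverse events between arms, yet the plain term for the condition is missing, and so is syncope. The list holds one postural subtype plus symptoms that can have many other causes. Followed as written, the rule scores a subject with vertigo as an event and a subject with syncope as none.

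This is the only between-arm test of hypotension-related adverse events that SAP 7.9 names. SAP 1.1 says the trial was designed to confirm an enhanced antihypertensive effect of the combination. Excess blood pressure lowering is therefore a natural safety question, and this row is one of the places a reader would look for it.

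**Working it through.** The plan gives no event rate, power or sample size for this category, so there is no figure to reproduce. The check is a comparison of texts, followed by an illustration of size.

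**Texts side by side**

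- Protocol 8.4: four named terms, open wording.
- SAP 1.3.9b and 6.4: five PTs, closed wording, the same list in both places. Hypotension and syncope are in neither.
- SAP 6.4, oedema events: the neighbouring list is built the same way but includes the base term, oedema, alongside its variants. No reason is given for treating hypotension differently.
- Protocol Appendix F, label 5.1: "Symptomatic hypotension is possible, particularly in patients with severe aortic stenosis".
- Protocol Appendix F, label 6.1: syncope is listed in its own right, in a cardiovascular group that includes "bradycardia, chest pain, peripheral ischemia, syncope, tachycardia, vasculitis". Vertigo and dizziness are reported elsewhere in the same section.
- The SAP's only coding remark covers light-headedness. Nothing says that hypotension or syncope would be coded to one of the five listed terms.

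**Illustration of size**

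Inputs:
- About 105 subjects randomised 3:3:1 (protocol section 3), so 105 × 3/7 = 45 in each amlodipine arm and 90 in the two together.
- A syncope rate of 0.1% to 1%. This is the label's frequency band, assumed to apply here. It is not specific to 14 days of dosing.

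One reclassified subject changes an arm's rate by 1/45 = 2.2 percentage points.

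Expected subjects with syncope = 90 × p. Chance of at least one = 1 − (1 − p)^90.

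| Assumed rate p | Expected among 90 | Chance of at least one |
|---|---|---|
| 0.1% | 0.09 | 8.6% |
| 0.5% | 0.45 | 36.3% |
| 1% | 0.9 | 59.5% |

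SAP 3.2 reports a realised ratio of 6:6:1. Applied to 105, that gives 105 × 6/13 = 48.5 per amlodipine arm, or about 97 in both. The expected range is then 0.097 to 0.97, which is essentially unchanged.

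For scale, the label gives dizziness, a listed term, at 3.4% on 10 mg: 45 × 0.034 = 1.53 expected per arm. At the label's rates, dizziness alone would outnumber syncope.

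**Effect on the test**

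With 45 per arm and a two-arm Fisher test, 2 versus 2 gives p = 1.0. Adding one subject to one arm (3 versus 2) still gives p = 1.0. Starting from no events in the other arm, 5 versus 0 gives p = 0.056 and 6 versus 0 gives p = 0.026. Fewer than one expected extra subject would rarely change the result.

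The documents give no rate for hypotension as an adverse event, so its contribution cannot be computed.

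**The case against.** The strongest reply has four parts.

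First, the harm is measured directly. Under SAP 6.4 and 7.9, orthostatic hypotension is recalculated from readings, tabulated at Days 0, 7 and 14, and tested between arms. The supine and standing pressures and resting clinic pressure are compared by ANCOVA. This stands and limits the point. It covers scheduled visits only, so it does not replace reported symptomatic hypotension or syncope between visits.

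Second, the omitted events are not lost. A reader might infer that hypotension and syncope go uncounted in this trial. The documents do not support that: SAP 7.9 tabulates all TEAEs by SOC and PT, with separate tables for serious events, adverse drug reactions and discontinuations. What is lost is their place in this category and its test. SAP 7.9 names no between-arm test at the level of individual PTs.

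Third, the SAP names more terms than the protocol did. It adds orthostatic hypotension and dizziness postural, so as a comparison with the protocol list the claim to be more comprehensive is fair. Comparability with the prior trial is also a legitimate reason to keep the five terms. Neither reason explains why the closed list leaves out the base term, and neither prevents a second row.

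Fourth, the label evidence is modest. The warning singles out severe aortic stenosis, and exclusion criterion 12 removes current cardiovascular disease other than hypertension. The label adds that acute hypotension is unlikely because onset is gradual. Syncope is listed among events of uncertain causality. The hypotension row in protocol Appendix C belongs to a general toxicity scale and does not show that such events were expected. All of this bears on how often the gap would matter, and it supports calling the effect small.

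**Conclusion.** The omission is real, appears in both places that define the category, and is worth correcting. Its scope is one secondary safety tabulation and its test. Only subjects with hypotension or syncope and none of the five listed terms are affected. On the label's band for syncope, 0.09 to 0.9 such subjects would be expected among 90 on amlodipine, and the upper end is probably generous for 14 days of dosing.

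Two assumptions carry this. One is that the label band applies here. The other is that hypotension and syncope are coded as PTs separate from the five listed; the documents support this only indirectly, through the label's separate entry for syncope.

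Two stronger readings should be resisted. A reader might infer that this is an efficacy-type endpoint which would conceal a difference between arms. It has no stated power, and the small expected counts do not support that. A reader might also want presyncope or decreased blood pressure added. The documents do not use either as an adverse event term, so they give no basis for those additions.

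**What to change.** In SAP 1.3.9b, 6.4 and 7.9:

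- Keep the five-term row as the SAP's specified comparison and for comparability with KIT-302-03-01.
- Add a second row made up of the five terms plus the PTs hypotension and syncope, with the same Chi-square or Fisher test.
- Label the second row as added after unblinding. SAP 1.5 identifies v4.0 as the final post-unblinding version, so the wider list must not replace the five-term list as the main test.
- Qualify the statement that the list "provides a more precise and comprehensive analysis": it is wider than the terms named in protocol 8.4, but it leaves out hypotension and syncope.

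The cost is two terms in one program and one table row. The drawback is a post hoc comparison that has to be disclosed as such in the study report.

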### **UAE**

Per the protocol, an UAE is one for which the nature or severity of the event is not consistent with the applicable study drug information [i.e., the most current version of the Investigator's Brochure (IB), the current product labeling for amlodipine tablets, and the current product labeling for celecoxib capsules] or listed in the protocol (as provided below).

This study was to enroll older subjects with existing hypertension. To that end, PTAEs and TEAEs could be expected due to the subjects' age and underlying conditions. These include: hypertension, hypertensive crisis, myocardial infarction, congestive heart failure, stroke both hemorrhagic and ischemic, any adult forms of cancer, and gastrointestinal ulcerations with complications including hemorrhage and perforation.

By definition, PTAEs initiate prior to administration of the first dose of study drugs, and thus a comparison against study drug specific risk information is inappropriate for determining expectedness

of PTAEs. Thus, only AEs that can be expected due to subject age and underlying conditions are relevant for the expectedness determination for PTAEs.

### **TEAE leading to discontinuation**

A TEAE leading to discontinuation is a TEAE with ‘the Primary Reason for discontinuation’ equal to “Treatment Emergent Adverse Event” on the Study Termination CRF.

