Study Day 28: Subjects will return to clinic on Day 28 for their final study visit (follow-up visit). The diary will be reviewed for any concomitant medications taken since the prior visit. Subjects will be solicited for history of TEAEs since the previous visit. A targeted physical examination will be performed and vital signs will be measured. For subjects whose study drugs are discontinued at Day 7, this follow-up visit will still occur on Day 28 (i.e., these subjects will return to the clinic for both the Day 14 and Day 28 visits).

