6. Collect the ABPM and download the systolic and diastolic BP values obtained by the ABPM and incorporate into the subject's medical record and CRF;
7. Orthostatic hypotension evaluation (see Section 8.4);
8. 12-lead ECG;

9. Blood sampling for hematology and serum chemistry (see Appendix B for list of tests);
10. Collection of urine for urinalysis (see Appendix B for list of tests);
11. Urine pregnancy test for WCBP only;
12. Blood sample will be collected at 24 hours \pm 1 hour post-dose for measurement of amlodipine concentrations. Only subjects enrolled at Investigational Sites that have UV-shielded lights will participate in the PK blood collections. Due to the design of the trial (randomized, double-blind, placebo-controlled), this blood sample will be collected and analyzed for all participating subjects, regardless of whether they are in a treatment arm that receives amlodipine.

Following the Day 14 evaluations, the following procedures will be performed:

1. Instruct subjects to resume taking their prescribed BP medication as directed by the study doctor or general practitioner;
2. Instruct subjects to continue to not take any NSAIDs or investigational drugs for the remainder of the study (through Day 28);
3. For WCBP: Instruct subjects to continue to use adequate contraceptive methods for the remainder of the study (through Day 28);
4. Subjects will be provided back their diary and instructed to record any concomitant medications taken between visits;
5. Subjects will be instructed to return to the clinic in 14 days (Day 28) for final study visit (follow-up visit), and to bring the completed diary to the visit.

6.7 Study Day 28

Subjects will return to clinic on Day 28 for their final study visit (follow-up visit). The following evaluations will be performed:

1. Solicit history of TEAEs since last visit;
2. Review diary for details of concomitant medications taken since last visit;
3. Targeted physical examination (see Section 8.2);
4. Vital signs (BP, pulse rate, respiration rate, and oral body temperature).

For subjects whose study drug is discontinued at Day 7, this follow up-visit will still occur on Day 28 (i.e., these subjects will return to the clinic for both the Day 14 and Day 28 visits).

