8.1.6 Routine Reporting of Adverse Events

PTAEs and TEAEs, whether or not associated with study drug administration, will be recorded on the AE form of the CRF and will be submitted to the Sponsor at regularly scheduled intervals.

The information to be entered in the CRF will include:

1. Medical diagnosis of the event in standard medical terminology (if a medical diagnosis cannot be determined, a description of each sign or symptom characterizing the event);
2. Date of onset of any new AE or the worsening of a previously observed AE. For the days when the subject is in the clinic, the time (based on a 24-hour clock) of onset should be recorded if available;
3. Date of resolution of the event (or confirmation ongoing). For the days when the subject is in the clinic, the time (based on a 24-hour clock) of resolution should be recorded if available;
4. Whether the event is serious (per definition in Section 8.1.1.2), and if so, the reason it is considered serious;
5. Severity of AE (per definitions in Section 8.1.2);
6. Assessment of the relationship of the AE to the study drug (per definitions in Section 8.1.3). Relationship assessments will only be made for TEAEs;
7. Whether the event is expected (per definition in Section 8.1.4);
8. Action taken in treating the AE (including concomitant medications or therapies administered) and/or change in study drug administration or dose (including whether the Study Drug was temporarily interrupted or discontinued);
9. Outcome of AE (recovered/resolved, recovered/resolved with sequelae, not recovered/not resolved, fatal, or unknown). Fatal should only be used when death is possibly related to the AE. If an outcome for an AE is not available at the time of the initial report, follow-up will proceed until an outcome is known or followed up to the final study visit. Any subject with a possible study drug-related TEAE at the final study visit will be followed until resolution or stabilization of the event. Further, any serious TEAE, whether or not related to study drugs that occurs within 14 days following the last dose of study drugs will be followed until resolution or stabilization of the event.

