APPENDIX A: SCHEDULE OF EVENTS

Event	Screening		Baseline/ 1 st Dose	Remainder of Treatment Period			Follow-up	
	Initial Screening Visit	Final Screening Visit	Day 0	Day 6	Day 7	Day 13	Day 14 ^(a)	Day 28 ^(a)
	Day -14 to -10	Day -1						
Informed consent ^(b)	X							
Record demographic data	X							
Complete medical history	X							
Monitor for pretreatment adverse events (PTAEs) ^(k)	X	X	X					
Record prior medications	X	X	X					
Record concomitant medications (CM)			X	X	X	X	X	X
Height and BMI	X							
Body weight while only wearing underwear and a light gown	X		X		X		X	
Comprehensive physical examination ^(c)	X						X	
Targeted physical examination ^(d)			X		X			X
Vital Signs ^(e)	X ^(e)		X		X		X	X
Provide ABPM and instruct on use		X		X		X		
25-hour monitoring of BP via ABPM ^(f)		X		X		X		
Orthostatic hypotension evaluation			X		X		X	
12-lead ECG	X						X	
Hematology ^(g)	X						X	
Serum chemistry ^(g)	X		X		X ^(g)		X	
Serum pregnancy test ^(h)	X							
Urine pregnancy test ^(h)							X	
Urinalysis ^(g)	X						X	

Event	Screening		Baseline/ 1 st Dose	Remainder of Treatment Period			Follow-up	
	Initial Screening Visit	Final Screening Visit	Day 0	Day 6	Day 7	Day 13	Day 14 ^(a)	Day 28 ^(a)
	Day -14 to -10	Day -1						
Urine drug screen ^(g)	X							
Review inclusion/exclusion criteria	X	X	X					
Randomization ⁽ⁱ⁾			X					
Administer study drug in clinic ⁽ⁱ⁾			X	X		X		
Provide diary to record CMs and study drug details			X					
Review diary				X	X	X	X	X
Collect study drug containers/capsule count				X	X	X		
Monitor for treatment emergent adverse events (TEAEs) ^(k)			X	X	X	X	X	X
Blood collection for PK ^(l)							X	

- a. If a subject is discontinued from study drug early, all study evaluations described for Day 14 and Day 28 will be performed if feasible. Study drug-related AEs (adverse reaction or suspected adverse reaction per the definitions in Section 8.1.3) will be followed until resolution or stabilization.
- b. ICF must be signed prior to performing any other screening evaluations
- c. Comprehensive physical examination will include the following organ or body system assessments: skin; head, eyes, ears, nose, and throat; thyroid; lungs; cardiovascular; abdomen (liver, spleen); lymph nodes; and extremities, as well as an abbreviated neurological exam

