### 7.4. Patients Disposition

Disposition of patients will be presented by treatment group and overall for all patients (i.e., the Overall Trial population will be used). The summary will include the number of patients at the Initial Screening Visit, Final Screening Visit, and Day 0 visit (including patients that were not randomized), the number of patients randomized, and the number of patients at each of the remaining visits (Days 6, 7, 13, 14 and 28).

The number of patients included in each of the randomized, safety, ITT, mITT, PP and PK populations will be summarized for each treatment and overall.

The number of patients who completed the study, the number of patients who completed study treatment, and the number of patients who discontinued from the study prematurely after randomization will also be presented by treatment group and overall for the randomized population. This summary will also include a breakdown of the primary reason for discontinuation following the categories on the CRF (i.e., TEAE, withdrawal of consent, lost to follow-up, protocol deviation, study terminated, and other).

Major and minor protocol violations will be presented in the listings only.

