Similar tabular summaries will be produced for each of the following: treatment emergent SAEs, ADRs, oedema events, other PTs of interest, treatment emergent UAEs, TEAEs leading to discontinuation, PTAEs, PTAEs leading to discontinuation, and pre-treatment SAEs. In the case of the latter two, the summaries will not be produced if there are no PTAEs leading to discontinuation or pre-treatment SAEs, respectively. For the ADR summary, if an ADR is reported more than once for a given subject, the worst-case attribution will be presented in the summary table.

A comparison of TEAE rates between the amlodipine + celecoxib and amlodipine + placebo arms will be performed using an exact logistic regression model with the TEAE ("1"=At least one TEAE occurred for the patient; "0"=otherwise) as dependent variable and treatment (amlodipine + celecoxib and amlodipine + placebo) as fixed effects. The probability modeled will be TEAE="1". The number of patients and the number of patients considered in the model will be provided. The exact odds ratio of the fixed effects will be calculated (amlodipine + celecoxib and amlodipine + placebo) with the relative 95% CI and p-value.

The same model will be repeated by considering treatment-emergent SAE (“1”=At least one treatment-emergent SAE occurred for the patient; “0”=otherwise) as dependent variable, with the caveat that if no treatment-emergent SAEs are reported the table will not be produced.

The rates of oedema events between the amlodipine + celecoxib arm and the amlodipine + placebo arm will be compared using an exact logistic regression and reporting the odds ratio. Oedema event (1 = at least one TEAE with PT of oedema, oedema peripheral, peripheral swelling, swelling, or joint swelling occurring for the subject; 0 = otherwise) will be the dependent variable, and treatment (amlodipine + celecoxib and amlodipine + placebo) will be the fixed effects.

The Fisher’s exact test will be run to compare the number of oedema events that occurred while on treatment (Day 0 to Day 14+1) and post-treatment (>Day 14+1) between treatment arms 1 and 2 (amlodipine + celecoxib and amlodipine + placebo).

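### The fixed Day 14+1 cut labels new oedema after an early stop as on-treatment, and TEAEs leading to discontinuation are identified only from the Study Termination form

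*SAP*

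**What the plan says.** **Oedema split.** SAP 1.3.9a and 7.9 plan a Fisher's exact test, arm 1 against arm 2, on the number of "oedema events that occurred while on treatment (Day 0 to Day 14+1) and post-treatment (>Day 14+1"). The cut is the same study day for all subjects. A separate exact logistic regression compares the two arms on any oedema TEAE.

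**Early stops.** Protocol Appendix A, note a: "If a subject is discontinued from study drug early, all study evaluations described for Day 14 and Day 28 will be performed if feasible". Protocol 3 adds: "For subjects whose study drugs are discontinued at Day 7, this follow-up visit will still occur on Day 28". A subject stopped at Day 7 for high BP has already taken that morning's dose at home and is told to resume the prescribed BP medication (Protocol 6.4).

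**Last dose.** SAP 5 takes the last-dose date from the Study Termination CRF, with the diary as fallback. It uses actual dates for treatment duration. The TEAE definition in SAP 6.4 also runs from the last dose, for 14 days.

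**TEAEs leading to discontinuation.** SAP 6.4: "A TEAE leading to discontinuation is a TEAE with ‘the Primary Reason for discontinuation’ equal to “Treatment Emergent Adverse Event” on the Study Termination CRF". SAP 7.9 reports this category by event, SOC and PT, and tests it between groups. For each AE, Protocol 8.1.6 has the CRF record action taken, "including whether the Study Drug was temporarily interrupted or discontinued".

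**Disposition.** SAP 7.4 counts study completers, "the number of patients who completed study treatment, and the number of patients who discontinued from the study prematurely after randomization". It gives reasons only for discontinuation, using the CRF categories.

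**The concern.** The outer end of the TEAE window moves with each subject's last dose, but the line inside it between on- and post-treatment does not. For an early stopper, oedema that first appears several days off study drug, possibly on another antihypertensive, is therefore labelled on-treatment. Oedema matters in this trial because Protocol 1 cites a lower oedema rate on the combination in support of a diuretic-like effect of celecoxib.

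For discontinuations, SAP 6.4 takes a subject-level reason from one form and uses it to define an event-level category. Stopping study drug and leaving the study are different things here, because early stoppers are asked back on Days 14 and 28. If a site enters such a subject as a study completer, there may be no primary reason to match. If the subject had several TEAEs, the reason may not identify the one responsible. The neighbouring definitions of SAE, ADR and fatal AE in SAP 6.4 all use the AE form event by event.

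**Working it through.** The plan states no figure on this point, so there is nothing to reproduce. The check is a count of days.

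**Inputs.** Planned doses on Days 0-13 (Protocol 5.3). TEAE window to 14 days after last dose (SAP 6.4). On-treatment through Day 14+1 = Day 15 (SAP 7.9). Last dose on Day 7 for a Day 7 stop (Protocol 6.4).

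**Formula.** For a last dose on Day k, the TEAE window ends on Day k + 14. Post-dose days labelled on-treatment = min(14, 15 − k); the rest of the 14 are labelled post-treatment.

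| Last dose (k) | TEAE window ends | Post-dose days labelled on-treatment | Labelled post-treatment |
|---|---|---|---|
| Day 1 | Day 15 | 14 | 0 |
| Day 3 | Day 17 | 12 | 2 |
| Day 7 | Day 21 | 8 (Days 8-15) | 6 (Days 16-21) |
| Day 10 | Day 24 | 5 | 9 |
| Day 13 (completer) | Day 27 | 2 | 12 |

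From Day 1 onward, an early stopper gets (15 − k) − 2 = 13 − k more off-drug days in the on-treatment period than a completer. For a Day 7 stop that is 6. This difference does not depend on which lag one thinks is right.

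**Under a last-dose rule with lag L.** On-treatment ends on Day k + L.
- L = 2: completer, 13 + 2 = Day 15, unchanged. Day 7 stop, 7 + 2 = Day 9, so Days 10-15 (6 days) move to post-treatment.
- L = 0: completer, Day 13 (2 days move). Day 7 stop, Day 7 (8 days move).
- L = 4: completer, Day 17 (2 days are added). Day 7 stop, Day 11 (4 days move).

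The amlodipine label in Protocol Appendix F gives a terminal half-life of about 30-50 h. Two days is 48/50 = 0.96 to 48/30 = 1.6 half-lives, so L = 2 is a choice, not a derived value.

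**Discontinuation category.** No count of affected subjects can be derived. As a scale only: 105 subjects at 3:3:1 gives 105 × 3/7 = 45 per amlodipine arm, so each uncounted TEAE would lower that arm's rate by 1/45 = 2.2 percentage points. SAP 3.2 reports that the realised ratio was 6:6:1. With 105 subjects assumed, that is 105 × 6/13 ≈ 48 per arm, and 1/48 = 2.1 points.

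**The case against.** The strongest reply concerns the discontinuation category. Protocol 4.3 makes an AE that poses unacceptable risk a withdrawal from the study, with date and reason entered on the CRF, even though the Day 14 and Day 28 evaluations go ahead. Attending Day 28 therefore should not turn that subject into a completer without a reason. Protocol 10.4 asks for TEAEs leading to study withdrawal, which is what SAP 6.4 implements. The Study Termination CRF is not in the documents. It also carries the last-dose date, and the SAP 6.4 definition of a PTAE leading to withdrawal suggests that it may name the event. Action taken is listed for every TEAE in any case. All of this stands: a reader might infer that treatment-ending TEAEs will go uncounted, but the documents show only that they could.

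On oedema, a reader might infer that subjects who stopped because of oedema are misplaced. They are not, because that oedema began on drug and is on-treatment under either rule. Nor do the prior-study rates of 15.6% and 8.2% measure the effect, since they are total rates that the split leaves unchanged. Some lag after the last dose is also reasonable given the half-life. What remains is that the fixed cut gives different subjects different lags.

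It is also tempting to say that BP-limit stops are invisible by arm. Visit counts, treatment completion and the Day 6-7 ABPM ranges, all by arm, show them in part.

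**Conclusion.** The oedema split is wrong as written for anyone who stops early: 8 post-dose days count as on-treatment for a Day 7 stop against 2 for a completer. The consequence is narrow. It concerns only new oedema that starts off drug up to Day 15, and only the on/post-treatment Fisher test. The exact logistic comparison and all efficacy analyses are unaffected. Its numerical effect cannot be stated, because the documents give neither the number of early stops nor the number of oedema onsets after them.

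It would go too far to say that the SAP defines stopping by calendar day in general, since treatment duration uses actual dates and treatment completion is counted separately.

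The definition of a TEAE leading to discontinuation is a lesser, conditional weakness. SAP 6.4 gives no event-level link for a category tabulated by event, and it relies on how a form outside the documents is completed. An undercount is possible, not shown.

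**What to change.** 1. In SAP 1.3.9a and 7.9, define on-treatment oedema as onset from first dose to the subject's actual last-dose date (SAP 5) plus one stated lag, and later onset as post-treatment. A lag of 2 days leaves the cut at Day 15 for subjects who took the Day 13 dose. State it as an assumption and vary it in a sensitivity run.
2. Keep the table of TEAEs leading to study withdrawal that Protocol 10.4 requires. Add a table of TEAEs leading to study drug discontinuation, taken from the action-taken field of the AE CRF whether or not the subject completed the study. Reconcile the two.
3. Optionally, add a disposition line by arm for study drug stopped above the SBP24h/DBP24h limit, from ABPM data already collected. Protocol 4.3 lists this reason separately from AEs; the SAP 7.4 categories do not.

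The documents describe all of these fields as collected, so the cost is SAP wording and a small amount of programming. SAP v4.0 is the post-unblinding version (SAP 1.5), so the changed and added outputs must be labelled as specified after unblinding. The planned Fisher test should be shown beside the revised one.
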